2.6 Known and potential risks and benefits

Hypotension

Empagliflozin causes intravascular volume contraction. Symptomatic hypotension may occur after initiating empagliflozin particularly in patients with renal impairment, the elderly, in patients with low systolic blood pressure, and in patients on diuretics. Before initiating empagliflozin, assess for volume contraction and correct volume status if indicated. Monitor for signs and symptoms of hypotension after initiating therapy and increase monitoring in clinical situations where volume contraction is expected

Impairment in Renal Function

Empagliflozin increases serum creatinine and decreases eGFR. The risk of impaired renal function with Empagliflozin is increased in elderly patients and patients with moderate renal impairment. More frequent monitoring of renal function is recommended in these patients renal function should be evaluated prior to initiating empagliflozin and periodically thereafter.

Hypoglycemia with Concomitant Use with Insulin and Insulin

Secretagogues

Insulin and insulin secretagogues are known to cause hypoglycemia. The risk of hypoglycemia is increased when empagliflozin is used in combination with insulin secretagogues (e.g., sulfonylurea) or. Therefore, a lower dose of the insulin secretagogue or insulin may be required to reduce the risk of hypoglycemia when used in combination with empagliflozin.

Genital Mycotic Infections

Empagliflozin increases the risk for genital mycotic infections. Patients with a history of chronic or recurrent genital mycotic infections were more likely to develop mycotic genital infections. Risk for female genital infection is 5.4%

(versus 1.5% with placebo). Management includes monitoring and treatment as appropriate.

Urinary Tract Infections

Empagliflozin (10mg) increases the risk for urinary tract infections (UTI) including pyelonephritis and sepsis due to urinary tract infections. The risk for UTI increases with age and with female sex. Risk for UTI is 9.3% (versus 7.6% with placebo). Management includes monitoring and treatment as appropriate.

Increased Low-Density Lipoprotein Cholesterol (LDL-C)

Increase in LDL-C can occur with empagliflozin. Monitor and treat as appropriate.

Macrovascular Outcomes

There have been no clinical studies establishing conclusive evidence of macrovascular risk reduction with empagliflozin or any other antidiabetic drug.

3 Trial Objectives and Purpose

We hypothesize that the effect of empagliflozin on the rate of cardiovascular death may be mediated by a direct effect on the risk for arrhythmic events (via a direct or an indirect effect on the myocardium). The current study aims at assessing the effect of empagliflozin on arrhythmias in diabetic patients with heart failure with reduced EF and relatively high arrhythmic burden.

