Collection of information on standard of care treatment will be done as part of medications records during the study.

17. Invite study subject to study site for Holter ECG installation in one of the 7 days before the next visit.

Base line visit (2) (day 0 ±7 days)

1. Patient's enrollment. Eligibility for the study according to inclusion and exclusion criteria will be rechecked but lab tests not repeated) if all criteria are fulfilled and there is no significant change in the subject's health, he/she will be enrolled into the study to receive the first study drug.
2. Get patient randomization number.
3. Begin study drug treatment (active or placebo), provide patient 60 tablets and give treatment instructions for home use.
4. Perform a complete physical examination.
5. Measure vital signs in order to ensure compliance with study criteria. Vital signs measurements will include systolic and diastolic blood pressure, pulse rate, respiratory rate, and body temperature. Body weight will also be measured. Measurements that may potentially constitute future adverse events (e.g. hypertension, fever etc.) should be graded in the medical history form at baseline according to CTC as described in [8.1.3 below](#)
6. Collect safety blood and urine samples. Including hematology and chemistry blood examinations and urine dipstick for signs of ketoacidosis or infection.
7. Review menopausal status and in women of childbearing potential perform a urine pregnancy test (β -HCG).
8. Collect home diary glucose results and provide a new diary for the following period.
9. Provide home diary for daily blood glucose determination.
10. Perform device interrogation.
11. Perform Monitor counter reset.
12. Collect Holter ECG device results and invite study subject to study site for Holter ECG installation in one of the 7 days days before the next visit.
13. Perform echocardiography for determination of EF
14. Consult endocrinologist for glucose lowering medication titration
15. Collect blood examination for NT-Pro-BNP
16. Collect urine and blood examination for biobank sample
17. Collect urine for electrolyte concentration

18. Obtain 24 hours urine sample collection
19. Perform cardiopulmonary exercise test (In case of inability to perform cardiopulmonary exercise test according to clinical judgment, patient will have a 6 minute walk distance test)
20. Perform 6 minute walk distance
21. Review concomitant medications.
22. Document adverse events.

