Treatment washout visit (3) (day 56 ±7 days)

1. Provide patient with 30 tablets of study drug for home use
2. Collect study drug blisters returned by patient.
3. Measure vital signs in order to ensure compliance with study criteria. Vital signs measurements will include systolic and diastolic blood pressure, pulse rate, respiratory rate, and body temperature. Body weight will also be measured.
4. Collect safety blood and urine samples. Including hematology and chemistry blood examinations and urine dipstick for signs of ketoacidosis or infection.
5. Remind patient to follow the endocrinologist instructions given on visit 2.
6. Collect venous blood that will be drawn for HbA1c.
7. Collect home diary glucose results and provide a new diary for the following period.
8. Perform device interrogation.
9. Perform Monitor counter reset.
10. Collect Holter ECG device results and invite study subject to study site for Holter ECG installation in one of the 7 days days before the next visit.
11. Perform echocardiography for determination of EF
12. Collect blood examination for NT-Pro-BNP
13. Collect urine and blood examination for biobank sample
14. Collect urine for electrolyte concentration
15. Obtain 24 hours urine sample collection
16. Perform cardiopulmonary exercise test (In case of inability to perform cardiopulmonary exercise test according to clinical judgment , patient will have a 6 minute walk distance test)

17. Perform 6 minute walk distance
18. Review concomitant medications.
19. Document adverse events.

Treatment visit (4) (day 84 ±7 days)

1. Provide patient with 60 tablets of study drug for home use
2. Collect study drug blisters returned by patient.
3. Measure vital signs in order to ensure compliance with study criteria. Vital signs measurements will include systolic and diastolic blood pressure, pulse rate, respiratory rate, and body temperature. Body weight will also be measured.
4. Review menopausal status and in women of childbearing potential perform a urine pregnancy test (β -HCG).
5. Remind patient to follow the endocrinologist instructions given on visit 2.
6. Collect home diary glucose results and provide a new diary for the following period.
7. Perform device interrogation.
8. Perform Monitor counter reset.
9. Collect blood examination for NT-Pro-BNP
10. Collect urine and blood examination for biobank sample
11. Collect urine for electrolyte concentration
12. Obtain 24 hours urine sample collection
13. Review concomitant medications

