8.1.2 Adverse events of Special Interest (AESIs)

The term AESI relates to any specific AE that has been identified at the project level as being of particular concern for prospective safety monitoring and safety assessment within this trial, e.g. the potential for AEs based on knowledge from other compounds in the same class. AESIs need to be reported to the Pharmacovigilance Department of Boehringer Ingelheim within the same timeframe that applies to SAEs.

Patients with AESIs need to be followed up appropriately, regardless of the origin of the laboratory data (e.g. central, local etc.). The Investigator should consider which, if any, concomitant therapies should not be taken during evaluation. Discontinued treatments can be reintroduced per Investigator discretion.

The following are considered as AESIs:

Hepatic injury

A hepatic injury is defined by the following alterations of hepatic laboratory parameters after randomisation:

- an elevation of AST and/or ALT ≥ 3 fold ULN combined with an elevation of total bilirubin ≥ 2 fold ULN measured in the same blood sample
- an isolated elevation of ALT and/or AST ≥ 5 fold ULN

These laboratory findings constitute a hepatic injury alert and the patients showing these abnormalities need to be followed up according to medical judgement. .

In case of clinical symptoms of hepatic injury (icterus, unexplained encephalopathy, unexplained coagulopathy, right upper quadrant abdominal pain, etc.) without laboratory results (ALT, AST, total bilirubin) available, the Investigator should make sure these parameters are analysed, if necessary in an unscheduled blood test.

Decreased renal function

Decreased renal function is defined by a creatinine value showing a ≥ 2 fold increase from baseline and is above the ULN.

For the AESI “decreased renal function”, the Investigator shall collect an unscheduled laboratory sample for creatinine as soon as possible and initiate follow-up laboratory tests of creatinine according to medical judgement.

Metabolic acidosis, ketoacidosis and diabetic ketoacidosis (DKA)

In case of metabolic acidosis, ketoacidosis and DKA further investigations should be done according to the medical judgment and the clinical course until a diagnosis is made and/or the patient is recovered.

DKA is defined by the diagnostic criteria in the table below, and as defined by the American Diabetes Association (ADA).

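### At visit 4, where the placebo-first half starts empagliflozin, no directed volume check and no creatinine is scheduled, although section 2.6 asks for a volume assessment first

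*Combined protocol and SAP*

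**What the plan says.** **Precautions.** On hypotension, section 2.6 says: "Before initiating empagliflozin, assess for volume contraction and correct volume status if indicated". It names patients on diuretics, the elderly, and those with renal impairment or low systolic pressure as at particular risk. On the kidney it says "Empagliflozin increases serum creatinine and decreases eGFR", and that "renal function should be evaluated prior to initiating empagliflozin and periodically thereafter".

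**Renal event of special interest.** Section 8.1.2 sets a creatinine threshold of at least 2, worded as a "fold increase from baseline and is above the ULN".

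**Visits.** In 4.2.2 the first treatment starts under the heading that begins "Base line visit (2) (day 0 ±7 days". The second starts under the one that begins "Treatment visit (4) (day 84 ±7 days". Table 2 marks the physical examination at visits 1 and 2 only, and the safety bloods, which include kidney function, at visits 1, 2, 3 and 5. The visit 4 list in 4.2.2 agrees with the table.

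**Washout.** The synopsis and 4.2 both place safety laboratory tests, HbA1c, device interrogation and reset, Holter and echocardiography at the end of washout, and then identify that point as visit 3.

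**The concern.** The trial starts a drug that contracts intravascular volume in patients with heart failure. The protocol's own precaution asks for volume status to be judged, and corrected if needed, before the drug is begun. In a crossover that moment comes twice: at visit 2 for one sequence and at visit 4 for the other. Visit 2 has a complete physical examination and safety bloods. Visit 4 has neither, and nothing tells the investigator to form a view on volume before dispensing.

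The missing chemistry also affects how later values are read. With no creatinine at the start of period 2, a change between visits 3 and 5 cannot be assigned from scheduled samples to the washout or to the second treatment. This is most awkward in the empagliflozin-first sequence, where the visit 3 value was drawn after 8 weeks on a drug that 2.6 says raises creatinine.

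The stake is patient safety at the second start, and the interpretation of period-2 laboratory changes. The primary endpoint, power and alpha are not touched.

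**Working it through.** **Number of patients.** Section 9.1 plans 64 per sequence, 128 in total. That figure reproduces. With an SD of differences of 40, a difference of 10, two-sided alpha 0.05 and 80% power, n = (40 × (1.960 + 0.842) / 10)² ≈ 126 by the normal approximation. The noncentral t with 126 degrees of freedom gives power 0.801 at 128. It is used here only to fix the 64 placebo-first patients.

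**Schedule.** Days are from Table 2; windows of ±7 days are from 4.2.2.

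| | Visit 2 | Visit 3 | Visit 4 | Visit 5 |
|---|---|---|---|---|
| Day | 0 | 56 | 84 | 140 |
| Range | −7 to 7 | 49 to 63 | 77 to 91 | 133 to 147 |
| Physical examination | yes | no | no | no |
| Safety bloods | yes | yes | no | yes |
| Vital signs, weight | yes | yes | yes | yes |
| NT-proBNP | yes | yes | yes | yes |

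**Gaps.** Each gap is the later day minus the earlier day. The minimum is the earliest later day minus the latest earlier day, and the maximum is the reverse. The first dose is taken to fall on the day of visit 4.

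- Last examination to first empagliflozin dose, placebo-first: 84 − 0 = 84 days; minimum 77 − 7 = 70; maximum 91 − (−7) = 98.
- Last creatinine to that dose: 84 − 56 = 28 days; minimum 77 − 63 = 14; maximum 91 − 49 = 42.
- That dose to the next creatinine: 140 − 84 = 56 days; minimum 133 − 91 = 42; maximum 147 − 77 = 70.
- Visit 3 to visit 5 creatinine, both sequences: 140 − 56 = 84 days; minimum 133 − 63 = 70; maximum 147 − 49 = 98. Nominally 28 of the 84 days (33%) are washout.
- Vital signs and weight at the start of period 2: gap 0.

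**Washout sentence against the schedule.** Visit 3 (day 56) opens the washout and visit 4 (day 84) ends it, so the timing phrase and the visit number cannot both be right. All the tests the sentence lists are scheduled at visit 3. Only device interrogation and reset are also scheduled at visit 4. The visit number therefore matches Table 2 and 4.2.2; the timing phrase does not.

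**The case against.** The strongest reply is that visit 4 is not empty. It takes systolic and diastolic pressure, pulse, weight, NT-proBNP, urine electrolytes and a 24-hour urine, and reviews medications and adverse events, all on the day of dispensing. Section 2.6 asks for an assessment of volume; it does not demand a full examination or chemistry, and it sits in the background text. No visit, visit 2 included, has a step labelled as the volume assessment. Section 4.3.1 already makes dosing conditional on there being no safety concern, extra tests may be ordered (end of 8.2.3, and 8.4.2), and 5.2 excludes eGFR below 45 and systolic pressure below 90 mmHg. All of this stands and lowers the weight of the point. What remains is that the entry limits are applied about 12 weeks earlier, the other safeguards are discretionary, and nothing at visit 4 turns the measurements into a decision.

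A reader might infer more than the documents support:

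- *That the renal precaution is broken.* It is not. The visit 3 creatinine precedes initiation. In the placebo-first sequence it follows 8 weeks of placebo and, under 4.2, precedes 4 more, so no change of study drug lies between it and visit 4.
- *That a renal event of special interest would be missed.* Visit 2 is titled the baseline visit and has bloods, so a doubling present at visit 5 is still found. Only its onset is unplaced. Section 9.2.2 grades laboratory values and plans no analysis of change from a period baseline, so no planned analysis fails.
- *That the washout sentence proves day-84 laboratory tests were intended.* The visit number fits the schedule, so the timing phrase is the likelier slip.
- *That visit 2 doses patients before sampling, because dispensing is listed first.* The lists are not stated to be chronological; visit 3 lists dispensing before the return of used blisters.

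**Conclusion.** The point holds as a minor safety-scheduling gap. For 64 of 128 planned patients, empagliflozin starts with a creatinine nominally 28 days old (14 to 42), a last scheduled examination 84 days old (70 to 98), and no instruction to judge volume status, although the relevant vital signs and weight are taken that day. For all 128, no creatinine marks the start of period 2. The washout sentence is internally inconsistent whichever half of it is the slip.

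This rests on three assumptions: that Table 2 and the 4.2.2 lists are the operative schedule, that dosing starts on the visit day, and that baseline in 8.1.2 means visit 2, which that section does not state.

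**What to change.** 1. At visit 4, in both sequences so that the blind is unaffected, run creatinine and serum electrolytes on the blood already being drawn.
2. Before dispensing at visit 4, have the investigator use the blood pressure, pulse and weight already taken, plus a brief clinical check, as a recorded volume assessment. If it is abnormal, correct volume status or withhold the tablets. If dispensing is delayed, move the counter reset to the day dosing starts.
3. Review the chemistry when it arrives and, if needed, interrupt study drug for safety under 4.4.2.
4. State that the visit 4 value is the reference for interpreting period-2 laboratory changes, and that the baseline for the renal event of special interest stays at visit 2.
5. Mark visit 4 for safety chemistry in Table 2 and add it to the 4.2.2 list. Reword the washout sentence in the synopsis and 4.2 so that visit 3 closes period 1 with its existing tests and the end-of-washout chemistry falls at visit 4.

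The cost is at most 128 panels and 128 brief checks, with no extra visit. The limit is that a chemistry result arriving after dispensing does not protect the first dose; only the volume check does.

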3.1 Primary Objective

The objective of the current study is to demonstrate the effect of empagliflozin compared to placebo on the rate of ventricular arrhythmic events in type 2 diabetes patients with heart failure with reduced ejection fraction and high risk arrhythmic profile.

3.2 Secondary Objectives

To evaluate the effect of Empagliflozin on cardiac function, using molecular (NT-Pro_BNP levels), echocardiographic and physiological markers of myocardial function.

4 Trial Design

4.1 Primary and secondary endpoints

4.1.1 Primary Endpoint

The primary endpoint is the burden of premature ventricular complexes, defined as the PVCs percentage of all beats in a pre-specified period captured on ICD or CRTD/P device.

PVC burden will be calculated according to device interrogation. In case of device failure to appropriately monitor the PVC burden, 24hr 12 lead holter ECG recording will be used as a complimentary method for arrhythmia assessment.

4.1.2 Secondary Endpoints

1. The number of non-sustained ventricular tachycardia (NSVT) episodes, defined as the NSVT number in a pre-specified period captured on ICD or CRTD/P device.
2. A composite cumulative endpoint of ventricular arrhythmia load (number of: sustained ventricular tachycardia, ventricular fibrillation, antitachycardia pacing (ATP) or delivery of shock therapy episodes, defined as the arrhythmias number in a pre-specified period captured on ICD or CRTD/P device.
3. The change in blood level of NT-Pro Brain Natriuretic peptide (BNP) from baseline to the end of any of the treatment periods
4. The change in Left ventricular end diastolic diameter on echocardiography from baseline to the end of any of the treatment periods.
5. The change in Left ventricular ejection fraction (EF) on echocardiography from baseline to the end of any of the treatment periods.
6. Safety.

4.2 Overall study design

The present study is a randomized, prospective, controlled, double blind, cross-over, pairwise, add on standard therapy, event driven study, comparing empagliflozin versus placebo on the ventricular arrhythmia burden in a blocked randomization stratified by ischemic versus non-ischemic cardiomyopathy and PVC burden at screening of $<$ or \geq to 4%.

Patients will be recruited from the congestive heart failure clinic of the study site and treated for up to 8 weeks with the study drug (or placebo) and then another 8 weeks with placebo (or study drug) with a washout period of 4 weeks between the two treatment periods. Potential study subjects will sign an informed consent prior to undergoing any study related procedure. Generally, study medications should be continued until intolerance. Treatment after completion of the study is at the discretion of the investigator.

Up to 128 patients are planned to be enrolled. Enrollment time of the study is one year.

This study encompass 4 periods for each study subject: screening period of 8 weeks, first treatment period of 8 weeks, washout period of 4 weeks and a second treatment period of 8 weeks. Expected duration of subject participation is 6-7 months.

Study assessments will be performed according the table of study procedures below. ([Table 2](#))

Screening / run in period

Patients will undergo screening for protocol eligibility within 56 days (8 weeks) of recruitment.

Subjects meeting all the inclusion criteria and do not meet any exclusion criteria will be enrolled after signing an informed consent.

Written informed consent must be obtained before any study specific medical procedures are performed. Evaluation consists of physical examination

including vital signs, laboratory-screening assessments including urine pregnancy test for FCBP, HbA_{1c}, device (ICD or CRTD/P) interrogation and echocardiography (if not done recently).

First treatment period

Randomization will take place after obtaining patient's informed consent and after fulfilling the inclusion and exclusion criteria. Patients will be assigned to empagliflozin or placebo treatment for a period of 8 weeks by a central randomization process.

Evaluations consists of vital signs, laboratory assessments blood examination, device (ICD or CRTD/P) interrogation, 24h' Holter ECG in case of ICD/CRTD/P malfunction as a backup arrhythmia assessment and echocardiography. Patient's glucose level will be monitored by a home device 3 times a day in the first week and thereafter once a week or as needed. At visit 2, an endocrinologist consultant will give to the patient instructions for antidiabetic treatment titration according to [appendix 1](#).

Patients will be treated for up to 8 weeks with the study drug or placebo 10 mg/day every morning.

Washout period

Study subjects will stop study drug (empagliflozin/placebo) of the first treatment period and will be given placebo for a washout period of 4 weeks and will crossover to the second drug at the end of this period at the beginning of the next treatment period. During this period, patient's glucose level will be monitored by a home device 3 times a day in the first week and thereafter once a week or as needed. Safety laboratory examinations, HbA_{1c}, device interrogation and resetting, Holter ECG and echocardiography will be performed at the end of this period (visit 3). In the case of abnormal glucose levels during the washout period, diabetes treatment will be changed according to appendix 1 aiming to maintain glucose levels at normal range.

Second treatment period

Patients will crossover to empagliflozin or placebo treatment for a period of 8 weeks.

Evaluations consists of vital signs, laboratory assessments including pregnancy test for FCBP. Patient's glucose level will be monitored by a home device 3 times a day in the first week and thereafter once a week or as needed. Device (ICD or CRTD/P) interrogation and 24h' Holter ECG in case of ICD/CRTD/P malfunction as a backup arrhythmia assessment and echocardiography. In the case of abnormal glucose levels during the second treatment period, diabetes treatment will be changed according to appendix 1 aiming to maintain glucose levels at normal range.

Patients will be treated for up to 8 weeks with the study drug or placebo 10 mg/day every morning.

Medication compliance will be performed during the two treatment periods by counting the returned study drug blisters.

Accompanying scientific program

In order to gain a deeper insight into the mechanism of action of empagliflozin in individuals with diabetes with heart failure and arrhythmogenic risk, additional research projects will be performed based on urine and blood samples of patients participating in this trial.

Additional samples will be drawn at different time points (visits 2-5) for the scientific projects, Furthermore, patients will be asked to agree, that the leftovers of the samples accompanying scientific program may be stored and used for other scientific analyses and projects. The following urine and blood examinations will be performed at the treatment periods: urine and blood biobank samples (This will require a separate IRB approval.), electrolytes urine examination, 24h urine collection, 6 minute walk distance and cardiopulmonary exercise test.

